3.2.5.2.3 Pharmacodynamics (PD) Parameters

The PD endpoints will be derived from the individual glucose profiles. The Baseline Glucose will be the last glucose measurement prior to time 0.

Actual Time will be used to the calculation of the following variables.

If insulin starts after receiving glucagon, the glucose values post insulin start will be censored out and considered as missing.

- Cmax : Maximum concentration of Glucose
- TMax : Time (in mins) when Glucose CMax is reached
- AUC₀₋₃₀: Area under the curve of Glucose from 0 to 30 minutes

- AUC₀₋₃₀ of Glucose will be calculated as the sum of areas of trapezoids, which are composed of adjacent Glucose values. The following rules will be considered:
 - If there are missing data points before the last observed value, they will be imputed as described in section 3.2.1
 - If there are missing data points after the last observed value, they will not be extrapolated and the AUC will be treated as undefined.
- AUC₀₋₁₈₀: Area under the curve of Glucose from 0 to 180 minutes
 - AUC₀₋₁₈₀ of Glucose will be calculated as the sum of areas of trapezoids, which are composed of adjacent Glucose values. The following rules will be considered:
 - If there are missing data points before the last observed value, they will be imputed as described in section 3.2.1.
 - If there are missing data points after the last observed value, they will not be extrapolated and the AUC will be treated as undefined.
- Time for plasma glucose to reach >70.0 mg/dL from receiving of glucagon.
 - The time stamp for 70.0 mg/dL will be imputed using linear interpolation between the two adjacent time points
- Time for plasma glucose to increase by at least 20 mg/dL from receiving of glucagon.
 - The time stamp for 20 mg/dL increase will be imputed using linear interpolation between the two adjacent time points

These PD parameters will be done based on both receiving glucagon and decision to dose.

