2.1.2 Sample Size

For the primary objective, a failure is recorded if the subject's plasma glucose fails to rise above 70.0 mg/dL within 30 minutes of administration of the dose of glucagon. Using this criterion, a sample size of 85 randomized subjects yields probabilities of G-Pen acceptance of 88% if the population failure rate differences of G-Pen and control are within 2%, and the rate of missing observations is within 5%.

Subjects will be recruited at approximately 6 clinical sites with a goal of no single center accounting for > 20% of the total sample.

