3.3.3.2.3 Pharmacodynamics Analyses

All of the PD parameters (as defined in section 3.2.5.2.2) will be presented descriptively.

A mixed model with treatment, period and sequence as fixed factors and subject as a repeated factor will be applied to compare the least square mean differences. Log transformation will be applied if skewness is observed. Unstructured covariance matrix will be used for the covariance matrix unless the model failed. In such case, structured covariance matrix will be selected based on the one given the smallest AIC (Akaike Information).

P-value for the difference test and 90% confidence for non-inferior test will be reported.

Additionally, mean glucose curve from 0 to 180 minutes post receiving glucagon will be presented graphically for each treatment. For this group of figures, the protocol defined time (section 3.2.1) will be used.

The mean glucose curve during hypoglycemia induction time will also be presented for each treatment. Since there is no protocol time for hypoglycemia induction stage, the mean glucose will be summarized for every 5 minutes based on the glucagon injection time.

This will be done based on the ITT population only, and will be done with time based on both “receiving glucagon” and “decision to dose”.

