3.3.3.2.5 Symptom relief of hypoglycemia

The time to symptom relief will be presented descriptively.

A survival analysis will be done to comparing the difference between treatment groups. P-value for the difference will be reported.

This will be done for ITT population only, and will be done with time based on both “receiving glucagon” and “decision to dose”.

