3.3.3.2.7 The time to first reporting of “no” for the global hypoglycemia question

The time to first reporting of “no” for the global hypoglycemia question will be summarized descriptively for each treatment. In rare cases if a subject does not answer “no,” the total time of 180 minutes will be used in the summary, but noted in the footnote.

A survival analysis will be done to compare the difference between treatment groups. P-value for the difference will be reported. Again, if a subject does not answer “no,” the total time of 180 minutes will be used, but noted as a censored value in the analysis model.

This will be done for ITT population only, and will be done with time based on both “receiving glucagon” and “decision to dose”.

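### The two glucose threshold times have no value when the threshold is not reached, so the planned mixed model compares crossers only

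*SAP*

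**What the plan says.** SAP section 3.2.5.2.3 lists two threshold times among the pharmacodynamic parameters, each measured from both T0 definitions (glucagon receipt and decision to dose).

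- Time to above 70.0 mg/dL: "The time stamp for 70.0 mg/dL will be imputed using linear interpolation between the two adjacent time points".
- Time to a rise of at least 20 mg/dL: "The time stamp for 20 mg/dL increase will be imputed using linear interpolation between the two adjacent time points".
- For all parameters in that section: "If insulin starts after receiving glucagon, the glucose values post insulin start will be censored out and considered as missing".

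No cap, censoring rule or other value is given for a threshold that is not reached. For AUC, by contrast, the same section says when the value is undefined.

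Section 3.3.3.2.3 covers all the PD parameters (it cites 3.2.5.2.2, but they stand in 3.2.5.2.3): "A mixed model with treatment, period and sequence as fixed factors and subject as a repeated factor will be applied". It adds a log transformation where the data are skewed, and then: "P-value for the difference test and 90% confidence for non-inferior test will be reported". Section 4.1 rules out imputation beyond what earlier sections specify.

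The symptom-based times are treated differently. For time to symptom relief, section 3.3.3.2.5 says: "A survival analysis will be done to comparing the difference between treatment groups". Section 3.3.3.2.6 does the same for time to minimal score. For a subject who never answers no to the global question, section 3.3.3.2.7 says: "the total time of 180 minutes will be used, but noted as a censored value in the analysis model".

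**The concern.** Interpolation needs one sample on each side of the threshold. Without a crossing there is no such pair and no time. The worst result on a time-to-recovery measure therefore becomes no result, and that subject-period cannot count against its drug in these two comparisons. Setting glucose after insulin start to missing can add further cases.

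The mixed model keeps the subject's other period, but its validity with incomplete data rests on values being missing at random. Here the value is absent because glucose did not rise far enough, so that basis does not hold.

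At stake are a p-value and a 90% interval for two secondary times. If one drug has more non-crossers, it is not shown as slower and may look slightly faster.

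**Working it through.** **Tracing the rules.** The SAP gives no figure for these times, so there is none to reproduce.

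1. A subject-period that crosses after 30 minutes, before any insulin start, is a primary failure but still has a threshold time. It stays in the model.
2. A subject-period that never crosses in the 180-minute follow-up has no adjacent pair, hence no time.
3. A subject-period that has not crossed when insulin starts loses its later samples, hence no time.
4. Section 3.3.3.2.3 has no censoring indicator and section 4.1 bars other imputation. Cases 2 and 3 drop out.

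**Inputs for the illustration.** From the SAP: 85 subjects, two-way crossover, and a model with treatment, period, sequence and unstructured covariance. Assumed: sequences of 43 and 42, lognormal crossing times with mean 15 min, CV 0.35, within-subject correlation 0.5, no true drug difference, and 1 or 2 non-crossers on one drug only. The test is two-sided 5%, so a drug should be declared faster in 2.5% of runs.

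**Which scale applies.** The skewness of a lognormal variable is (CV² + 3) × CV = (0.1225 + 3) × 0.35 = 1.09. Under the SAP's skewness rule such data would be log-transformed, so the log-scale column is the relevant one.

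**Results** (apparent advantage of the drug with the non-crossers, and share of runs in which it is declared faster):

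| Non-crossers | Which ones | Log scale | Untransformed |
|---|---|---|---|
| 1 or 2 | random | no distortion | 0.0 min |
| 1 | slowest | about 0.1 min; about 4% | about 0.2 min; about 4.5% |
| 2 | slowest | about 0.2 min; 5-6% | about 0.3 min; about 8% |

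The slowest-period case is close to a worst case for these counts: the lost values are exactly the longest ones, and all on one drug.

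**The case against.** The strongest reply is that little is lost. Non-crossing still shows in the primary failure score, the binary secondary endpoints and the counts in section 3.3.3.2.2. A non-crosser's low glucose also enters Cmax and AUC0-30 in the same PD analysis. Section 3.3.3.2.3 names no PD margin, so the 90% interval decides no non-inferiority claim. A time-to-event test would detect little with one or two extra non-crossers. All of this stands and keeps the point minor. It does not supply the missing rule.

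It is also fair that differing from the symptom-time sections is not in itself an error. Only section 3.3.3.2.7 states a censoring value. Those sections show that a suitable method is already in the plan, no more.

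Three stronger readings are tempting but not supported.

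- A reader might infer that the sample-size section bounds the imbalance at 0 to 2 subjects, since it assumes "population failure rate differences of G-Pen and control are within 2" percent and 0.02 × 85 = 1.7. A subset does not inherit a bound on a difference: failures of 3 against 3 allow non-crossers of 3 against 0. For the 20 mg/dL rise, non-crossers need not be failures at all, because a baseline above 50 mg/dL (70 − 20) can pass 70 without rising 20. The 1-2 used above is an assumption.
- A reader might set non-crossers to 180 minutes and report a shift of several minutes in the mean. The SAP defines no such restricted mean, and nothing in it shows that any subject-period stays at or below 70 mg/dL for 180 minutes.
- A reader might extend the criticism to AUC0-180. That parameter already has a stated rule for when it is undefined.

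**Conclusion.** The point holds as a minor defect in two secondary PD times. Followed as written, the plan leaves out subject-periods for a reason tied to the outcome, and its comparison applies to crossers only.

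The SAP does not determine the size. There is no distortion if non-crossers are absent or a random subset. If one or two on one drug are its slowest periods, the illustration gives about 0.1-0.2 min and about 4-6% declared faster instead of 2.5% on the log scale (about 0.2-0.3 min and 4.5-8% untransformed). These figures rest on the assumed mean, CV, correlation and number of non-crossers. The reading that non-response is hidden from the trial is not supported, for the reasons given under the objection.

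**What to change.** In sections 3.2.5.2.3 and 3.3.3.2.3:

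- Analyse both threshold times as time-to-event from T0, for each T0 definition.
- Censor non-crossers at the last usable pre-insulin sample, and state that censoring at insulin start assumes it is uninformative.
- Include treatment and period and allow for the within-subject pairing, for example with a Cox model using subject-clustered variance and a small-sample correction.
- Report by treatment the number of non-crossers and the number of insulin starts before crossing.
- Keep the least-squares mean difference only as a summary labelled 'crossers only'.

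The cost is SAP wording and a little programming, with no new data. The main result for these two times moves to a hazard-ratio scale. In simulations of the same kind, the clustered Cox test at nominal 5% had size 6.0-6.4%, or 5.4-5.9% with an n/(n−1) factor and t reference. Its power with 1-2 excess non-crossers was 6-12% if they were random and 4-5% if they were the slowest. The gain is a defined comparison with non-crossers visible, not power.

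As a separate wording point, section 3.3.3.2.2 asks for subgroup analysis of the number of subjects above 70 mg/dL and points to section 3.3.5.1, which lists a time in minutes. State which is meant and, if the time, how 30-minute failures are shown.

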3.2.5.2.4 Hypoglycemia Symptom Mean Scores

Symptoms of hypoglycemia are captured using the following questionnaire:

Neuroglycopenic Symptoms	Severity Score (1-6)
Dizziness	
Blurred vision	
Difficulty in thinking	
Faintness	
Autonomic Symptoms	Severity Score (1-6)
Sweating	

Neuroglycopenic Symptoms	Severity Score (1-6)
Tremor	
Palpitations	
Feeling of nervousness	
Overall Assessment of Hypoglycemia	Yes/No
Do you currently feel hypoglycemic?	

The following 3 Mean Scores will be calculated for each subject at each of the measurement time points:

1. Average Neuroglycopenic Symptom Score (ANS) :

$$\frac{\text{Dizziness} + \text{Blurred vision} + \text{Difficulty in thinking} + \text{Faintness}}{4}$$

2. Average Autonomic Symptom Score (AAS):

$$\frac{\text{Sweating} + \text{Tremor} + \text{Palpitations} + \text{Feeling of nervousness}}{4}$$

3. Average Total Symptom Score (ATS):

$$\frac{\text{Sum of all symptoms}}{8}$$

Overall Assessment of Hypoglycemia:

- This will be treated as a categorical variable, so no means will be calculated.

This parameter will be analyzed both on time from receiving glucagon and from a decision to dose.

3.2.5.2.5 Symptom relief

Symptom relief of hypoglycemia is defined as a return to a score (ANS, AAS and ATS) no more than one unit above baseline symptoms during the euglycemic baseline period, where the baseline symptom is the minimal values of score (ANS, AAS and ATS) prior to receiving glucagon (T0).

The time (min) to Symptom relief will be derived for analysis purpose. Actual Time will be used in calculation.

This parameter will be done based on both receiving glucagon and decision to dose.

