1.2.2 Secondary Objectives

The secondary objectives of this study are:

- To demonstrate the efficacy (either return to plasma glucose >70.0 mg/dL or an increase in plasma glucose ≥ 20 mg/dL within 30 minutes post study drug injection) of G-Pen 1 mg (test) to be non-inferior to Lilly Glucagon 1 mg (reference), in T1D subjects in a state of insulin-induced hypoglycemia.
- To demonstrate the efficacy (return to plasma glucose >70.0 mg/dL or alleviation of all neuroglycopenic symptoms at 30 minutes post study drug injection) of G-Pen 1 mg (test) to be non-inferior to Lilly Glucagon 1 mg (reference), in T1D subjects in a state of insulin-induced hypoglycemia.
- To compare the pharmacodynamics characteristics of G-Pen 1 mg (test) versus Lilly Glucagon 1 mg (reference) in T1D subjects who are in a state of insulin-induced hypoglycemia.
- To compare G-Pen (test) and Lilly Glucagon (reference) with regards to hypoglycemia symptom relief.
- To compare G-Pen (test) and Lilly Glucagon (reference) with regards to the preparation time required to inject to the abdomen from a decision to treat.
- To compare the safety and tolerability of G-Pen 1 mg (test) versus Lilly Glucagon 1 mg (reference) in T1D subjects who are in a state of insulin-induced hypoglycemia.

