3.2.5.2 Secondary Endpoints

3.2.5.2.1 Binary Responses

The following secondary response endpoints will be assessed. Mean (Dht) and SE (Dht) corresponding to these conditions will be evaluated based on the same system defined in section 3.2.5.1. The 30 minutes reference in this section will be the protocol time.

1. Return of plasma glucose to > 70 mg/dL or neuroglycopenic symptomatic relief within 30 minutes after receiving glucagon. The Baseline Glucose will be the last glucose measurement prior to time 0.
2. Return of plasma glucose to > 70 mg/dL or an increase in plasma glucose by ≥ 20 mg/dL within 30 minutes after receiving glucagon. The Baseline Glucose will be the last glucose measurement prior to time 0.
3. Increase in plasma glucose by ≥ 20.0 mg/dL within 30 minutes after receiving glucagon. The Baseline Glucose will be the last glucose measurement prior to time 0.
4. Neuroglycopenic symptomatic relief within 30 minutes after receiving glucagon.

Secondarily, this will be repeated with success/failure evaluated at a time point of 30 minutes from a decision to dose.

3.2.5.2.2 Number of subjects having glucose >70 mg/dL within 30 minutes of receiving glucagon

This will be the raw count of subjects at protocol time points: 5, 10, 15, 20, 25, and 30 minutes.

This analysis will be done both based on time from receiving glucagon and from a decision to dose.

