3.2.5.2.6 The time to the minimal score post dose

This will be calculated for sub-scales ANS, AAS and ATS as the difference (in mins) between the actual time when the minimal number is observed and the time of receiving glucagon. Actual Time will be used to the calculation of the following variables.

- Subjects who never develop symptoms will be assumed to have a value of 0.

This parameter will be analyzed both on time from receiving glucagon and from a decision to dose.

3.2.5.2.7 The time to first reporting of “no” for the global hypoglycemia question will be defined as below:

This will be calculated as the difference (in mins) between the actual time when the first “no” for “Overall Assessment of Hypoglycemia” is observed and the time receiving glucagon. Actual Time will be used to the calculation of the following variables.

- Subjects who never develop symptoms (never answers No) will be assumed to have a value of 0.
- In very rare cases, if subject answers Yes all the way to the last time point, the total time will be recorded. (And it will be analyzed based survival model.)

This parameter will be analyzed both on time from receiving glucagon and from a decision to dose.

3.2.5.2.8 The Glucagon Preparation Time:

Glucagon preparation time (min) is defined as the time between “decision to dose” and time of study drug administration to the abdomen. Actual Time will be used to calculate this variable.

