4.3 PROTOCOL VIOLATIONS

Potential protocol violations are incorporated into the definition of Per Protocol Population (see 3.1.2). This definition excludes from PP analysis any subject who has one of the following 4 major protocol violations:

1. Fails to meet all eligibility criteria.
2. Fails to meet the definition of hypoglycemia steady state prior to dosing at either treatment visit. A steady state of hypoglycemia is defined as two consecutive plasma glucose values between 43.0 and 49.9 mg/dL, and a linearly extrapolated 8-minute later glucose value \geq 42.0 mg/dL.
3. Fails to complete both treatment visits.
4. Fails to receive a dose of both test articles during the study (G-Pen and Lilly Glucagon).

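### Symptom relief needs no raised score at dosing, so response 1 can count a subject without raised symptoms as a success although glucose never exceeds 70 mg/dL

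*SAP*

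**What the plan says.** SAP 3.2.5.2.5 holds the only definition of relief in the document: "Symptom relief of hypoglycemia is defined as a return to a score (ANS, AAS and ATS) no more than one unit above baseline symptoms". The baseline is the lowest score recorded before T0. The section asks for no minimum score or rise at T0, and it has no rule for a subject whose score was not raised.

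SAP 3.2.5.2.1 uses relief in two binary responses. Response 4 is neuroglycopenic relief alone. Response 1 is "Return of plasma glucose to > 70 mg/dL or neuroglycopenic symptomatic relief within 30 minutes after receiving glucagon", so either route is enough. Both take the failure scores of the primary endpoint (3.2.5.1), and SAP 3.3.3.2.1 applies the same non-inferiority test to them in the ITT and PP populations. Response 1 serves a named secondary objective, which SAP 1.2.2 words as "return to plasma glucose >70.0 mg/dL or alleviation of all neuroglycopenic symptoms at 30 minutes post study drug injection".

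Neither population supplies the missing condition. ITT is everyone randomized (3.1.1). PP depends on the pre-dose steady state, which SAP 4.3 defines by glucose alone: "A steady state of hypoglycemia is defined as two consecutive plasma glucose values between 43.0 and 49.9 mg/dL", plus a condition on the extrapolated glucose value.

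The plan does foresee subjects without symptoms. For time to the minimal score, SAP 3.2.5.2.6 says: "Subjects who never develop symptoms will be assumed to have a value of 0". A similar rule stands in 3.2.5.2.7. There is none in 3.2.5.2.5.

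**The concern.** A relief endpoint is informative only where there is something to relieve. A subject-period that already meets the criterion at T0 says little about the drug, yet it counts as a success once one post-dose score stays within the limit. In response 1 the two routes are joined by an *or*, so this success overrides a glucose failure.

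If such subject-periods are equally common on both drugs, they lower both failure rates in proportion and so shrink the difference. In a non-inferiority comparison that favours acceptance. Response 1 could then meet the 0.1 margin partly because subjects had few neuroglycopenic symptoms at dosing, while the reader takes the result as evidence that G-Pen corrected hypoglycemia or relieved its symptoms.

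**Working it through.** **Inputs from the SAP.** ANS is the mean of four items, each scored 1 to 6 (3.2.5.2.4). N = 85; the stated acceptance probability is 88% for a failure-rate difference within 2% and missing data within 5% (2.1.2). Missing outcomes score 0.2 for G-Pen and 0.1 for control (3.2.5.1). Non-inferiority is declared if mean D + 2.8 SE ≤ 0.1, with SE = SD/√N (3.3.3.1, 3.2.5.1).

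**Assumptions, not in the SAP.** The control failure rate is not stated. Nor is q, the share of subjects already within one ANS unit of baseline at T0.

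**The plan's own figure.** Simulating the paired score rule with 0% control failures, 2% G-Pen failures and 5% missing gives 87.2%, against the stated 88%. The rule is therefore read correctly. That figure concerns the primary endpoint and does not depend on the relief definition.

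**How wide the limit is.** With baseline ANS at its floor of 1.0, relief means ANS ≤ 2.0, that is, an item sum of 8 or less. Items 3, 2, 2, 1 at T0 give 8/4 = 2.0 and qualify. So do 5, 1, 1, 1. Of the 6⁴ = 1,296 possible patterns, 70 qualify. The gap therefore covers some symptomatic subjects as well as symptom-free ones.

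**How many failures the rule tolerates.** With no control failures and no missing data, k G-Pen failures give mean D = k/85 and SD = √[(85/84) × p(1 − p)], where p = k/85.
- k = 3: mean 0.0353, SD 0.1856, SE 0.1856/√85 = 0.0201; 0.0353 + 2.8 × 0.0201 = 0.092, accept.
- k = 4: mean 0.0471, SD 0.2130, SE 0.0231; 0.0471 + 2.8 × 0.0231 = 0.112, reject.

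The rule accepts with up to 3 failures.

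**Effect on response 1.** Take a 10% G-Pen glucose failure rate, symptoms independent of glucose, every subject in q having a qualifying post-dose score, and no one else succeeding through symptoms. The response 1 failure rate is then 0.10 × (1 − q), and acceptance is P(X ≤ 3) for X ~ Binomial(85, 0.10 × (1 − q)).

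| q | Response 1 difference | Acceptance |
|---|---|---|
| 0% | 0.100 | 2.5% |
| 20% | 0.080 | 8.4% |
| 30% | 0.070 | 14.6% |
| 50% | 0.050 | 38.0% |

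**Sensitivity to the control rate.** The same 10-point glucose gap taken as 12% against 2% (independent outcomes, simulated) gives about 1%, 4%, 8% and 26% at the same values of q.

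**At the planning difference.** With 2% against 0% and no missing data, acceptance is 91% at q = 0 and 95% at q = 20%. The gap matters little if G-Pen performs as planned and more if it does not.

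**The case against.** The strongest reply is that the definition speaks of a return, and a return needs an earlier departure. On that reading the status of a subject who was never raised is undefined, rather than defined as success. This stands in part. But the word is given no threshold, time point or score for those who never rose. One programmer could count them as relieved, another as failed, and another as missing at 0.2 or 0.1. The only test that can be programmed from the text is the level test, and it yields a success.

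Three stronger readings are tempting, and the documents do not support them.
- *Such subjects cannot fail.* They still need a qualifying post-dose score. A subject who worsens beyond the limit at every questionnaire within 30 minutes fails on symptoms, and a missing outcome is not scored 0 in ITT.
- *They enter time to relief as events at time zero by rule.* The value-0 rules belong to 3.2.5.2.6 and 3.2.5.2.7. Neither 3.2.5.2.5 nor 3.3.3.2.5 has one.
- *The 38% is a type I error rate.* SAP 3.3.3.1 sets the margin on the population mean failure-score difference. At q = 50% the response 1 difference as defined is 5 points, inside the margin. The figure shows that the endpoint is easier to meet, not that the test errs on its own terms.

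It is also fair that the damage is contained. The primary endpoint and responses 2 and 3 use glucose only and are reported alongside, so a response 1 result carried by subjects without raised symptoms would look out of line with them.

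**Conclusion.** The point holds for response 1, response 4 and time to relief. Relief is a level test with no condition at T0, no population supplies one, and the *or* in response 1 lets a score that was never raised override a glucose failure. For an endpoint with its own non-inferiority objective, that is a rule which can mislead, not just missing detail.

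The direction, towards acceptance, rests on symptom status being unrelated to treatment. The size is unknown: both the share already within the limit and the 0% control failure rate are assumed, so 2.5% rising to 38% is an illustration and not an estimate. Nothing here affects the primary endpoint. This should be settled before analysis, but it does not threaten the main conclusion.

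**What to change.** In SAP 3.2.5.2.1 and 3.2.5.2.5:
- **Flag.** Derive, for each subject-period, whether the last ANS before T0 is more than one unit above baseline. Take T0 as injection time or decision to dose, to match the analysis.
- **Response 1.** Let the relief route count only where the flag is met, and score all other subject-periods on glucose alone. Every subject keeps a paired difference and ITT stays intact. In the model above this returns acceptance to the q = 0 row.
- **Response 4 and time to relief.** Keep the ITT analysis and state how subject-periods that were not raised are entered. Add a supportive analysis limited to subjects with raised scores at T0 in both periods. Restricting the main analysis to raised subject-periods would leave some subjects without a paired difference.
- **Reporting.** Give the number not raised at T0 by treatment.

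Two wordings should be settled at the same time. SAP 3.2.5.2.5 ties baseline both to the euglycemic period and to the lowest score before T0, and the flag depends on which is meant. SAP 1.2.2 speaks of all neuroglycopenic symptoms at 30 minutes. The flag does not resolve that difference: a raised subject with baseline ANS 1.0 who ends at 5, 1, 1, 1 would still count as relieved.

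The cost is one derived flag from data already collected, some added wording, and a response 1 result that may be slightly less favourable.
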